7.6.1 Potential risks

The potential risks for the treatment with dapagliflozin and other SGLT2 inhibitors are described in the IB. Due to its mode of action resulting in increased urinary glucose excretion an increased risk of urinary tract infections (slightly higher compared to placebo in the phase III studies) and genital infections has been seen.

Based on the mechanism of action of dapagliflozin there may be a potential risk for this compound to cause hypovolaemia or electrolyte imbalance. As a precaution, patients who, in the judgment of the Investigator may be at risk for dehydration or volume depletion due to co-existing conditions or concomitant medications, such as loop diuretics, should have careful monitoring of their volume status. In patients already receiving dapagliflozin who develop conditions that may cause hypovolaemia or electrolyte imbalance, decisions to interrupt or discontinue dapagliflozin therapy and management of patients should be based on clinical judgment.

Higher proportions of patients with marked laboratory abnormalities of hyperphosphatemia were reported in dapagliflozin vs placebo. The magnitude and clinical significance of this in patients with CKD is unclear.

After the introduction of dapagliflozin and other SGLT2 inhibitors there have been post marketing reports of ketoacidosis, including diabetic ketoacidosis (DKA), in patients with type 1 diabetes (T1D) and T2D, although a causal relationship has not been established. Patients presenting signs and symptoms consistent with ketoacidosis, including nausea, vomiting, abdominal pain, malaise, and shortness of breath, should be assessed for ketoacidosis, irrespective of blood glucose levels. If ketoacidosis is suspected, discontinuation or temporary interruption of dapagliflozin should be considered and the patient should be promptly evaluated.

Predisposing factors to ketoacidosis include a low beta-cell function reserve resulting from pancreatic disorders (e.g., T1D, history of pancreatitis, or pancreatic surgery), insulin dose reduction, reduced caloric intake, or increased insulin requirements due to infections, illness or surgery and alcohol abuse. Dapagliflozin should be used with caution in these patients.

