Transplant-specific outcomes: CNI levels will be measured during the trial. All results of CNI monitoring will be communicated within 24 hours to the primary transplant nephrologist, in the event that dose adjustments to CNIs are required. In light of the data in native kidneys suggesting that tubulointerstitial hypoxia plays an important role in the development of DKD⁵⁰, all participants will be offered the opportunity to undergo a renal ultrasound (photoacoustic ultrasonography) at baseline (between day -7 and 0) prior to drug administration, and at the end of the study (between day 77 and 84) prior to drug discontinuation. This novel methodology uses spectroscopic photoacoustics to assess kidney ischemic damage using non-invasive ultrasonography (Vevo System, FujiFilm, VisualSonics Inc., Toronto). This tool determines the degree of tissue hypoxia, as measured by oxygen saturation, and has been shown to correlate with areas of renal tissue ischemia^{84, 85, 86}. In addition, the use of this methodology is ideal in KTR due to the anatomic proximity of the transplanted kidney, which is traditionally placed in the anterior abdomen (iliac fossa). This methodology has been previously used by [name] (coapplicant). Photoacoustic renal ultrasounds will be performed at SMH and incorporated into a study visit when possible, given the short distance (~ 2 kilometers) between TGH and SMH. This is an optional ultrasound for participants of the study.

Safety outcomes: The side effects of SGLT2i have been well described and will be assessed at each study visit. Adverse events include AKI, volume depletion, hyperkalemia, urinary and mycotic infections, ketoacidosis, amputations and allergic reactions. Episodes of biopsy-proven acute rejection (as defined by the Banff criteria), death-censored graft failure (defined as the need for initiation of chronic dialysis or re-transplantation) or death with graft function (defined as death with a functioning allograft) will also be collected. Kidney transplantation assures complete denervation of the transplanted kidney and the renal vasoconstrictive response in the setting of intravascular volume depletion is diminished in KTR. Therefore, frequent monitoring for adverse events has been integrated in our study design, occurring on 7 separate occasions, to capture these adverse events should they occur. Adverse event monitoring is shown in **Table 2** and will occur

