in person on study day 7 (1 week), day 42 (6 weeks), day 77 (11 weeks), day 84 (12 weeks) and day 91 (1 week after drug discontinuation) and by telephone/e-mail on study day 21 (3 weeks) and day 63 (9 weeks). All adverse events will be recorded on case report forms.

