10.2.3 Adverse events of interest

Urinary tract infections

Genital infections

Diabetic ketoacidosis (DKA)

Volume depletion (Eg, dehydration, hypovolemia, or hypotension)

Fractures

Major hypoglycaemic event

A major hypoglycaemic event is defined as an event that requires assistance of another person to actively administer carbohydrates, glucagon, or take other corrective actions. Plasma glucose concentrations may not be available during an event, but neurological recovery following the corrective actions is considered sufficient evidence that the event was induced by a low plasma glucose concentration.

Acute Kidney Injury

Acute kidney injury is defined as an increase of 40% in serum creatinine from the previous visit or hospitalization due to acute kidney injury.

Amputation:

Amputations will be recorded in the eCRF. We will report the underlying cause of amputation as the AE and include the information regarding the actual amputation in the AE description rather than reporting the amputation procedure as a separate AE.

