severe nausea, but not a SAE unless it meets the criteria shown in above. On the other hand, a stroke that results in only a limited degree of disability may be considered a mild stroke but would be a SAE when it satisfies the above criteria.

• Causality Collection

The Investigator will assess causal relationship between Investigational Product and each SAE/DAE, and answer 'yes' or 'no' to the question 'Do you consider that there is a reasonable possibility that the event may have been caused by the investigational product?'

• Adverse Events Based on Signs and Symptoms

All SAEs/DAEs/AE spontaneously reported by the patient or reported in response to the open question from the study personnel: 'Have you had any health problems since the previous visit/you were last asked?' or revealed by observation will be collected and recorded in the eCRF. When collecting SAEs/DAEs/AEs, the recording of diagnoses is preferred (when possible) to recording a list of signs and symptoms. However, if a diagnosis is known and there are other signs or symptoms that are not generally part of the diagnosis, the diagnosis and each sign or symptom will be recorded separately.

• Adverse Events Based on Examinations and Tests

The results from protocol mandated laboratory tests and vital signs will be summarised in the clinical study report. Deterioration as compared to baseline in protocol-mandated laboratory values, or vital signs should therefore only be reported as AEs if they fulfil any of the SAE criteria, are the reason for discontinuation of study treatment, or fulfil criteria of AEs of special interest. If deterioration in a laboratory value/vital sign is associated with clinical signs and symptoms, the sign or symptom will be reported as an SAE/DAE or AE and the associated laboratory result/vital sign will be considered as additional information. Wherever possible the reporting Investigator uses the clinical, rather than the laboratory term (e.g., anaemia versus low haemoglobin value). In the absence of clinical signs or symptoms, clinically relevant deteriorations in non-mandated parameters should be reported as AE(s).

Any new or aggravated clinically relevant abnormal medical finding at a physical examination as compared with the baseline assessment will be reported as an AE.

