hyperfiltration). This has also been part of previous mechanistic studies in the [name] Laboratory in patients with diabetes. ^bIn patients with T2D/PTDM ^c Renal ultrasound will be performed between visits 2 and 3 and between visits 8 and 9. ^c Lithium tablet will be taken at 10pm the night before Visits 3,4 and 9. *Study visits are subject to PI's discretion based on participants' condition/safety/lab results. HGM; home glucose monitoring; NICOM; Non-invasive cardiac output monitoring; EEOS; early end of study

Table 3:	Study variables	included in	data collection
----------	-----------------	-------------	-----------------

Category	Demographic &	Imaging	Physical	Adverse events	Laboratory	Laboratory
	medical history		examination		(Blood)	(Urine)
Category Variables	0 1	Imaging Tissue hypoxia ultrasound of allograft	-	Adverse events Hypotension, volume depletion, Hyper-kalemia, acute kidney injury, urinary infections, mycotic infections, amputation, allergic reaction, hypo-glycaemia, ketoacidosis	· ·	v
	history				cholesterol profile, CNI level, beta-HCG	
					catecholamines	

	Heart rate variability Arterial stiff- ness, aortic pulse wave velocity, cardiac output, stroke volume, total peripheral resistance	Death-censored graft failure, death with graft function, biopsy- proven acute rejection	Biomarker biobanking GFR (iohexol), 8-hydroxy- deoxyguanosine, 8-isoprostane	8-hydroxy- deoxyguanosine, 8-isoprostane, urine adenosine, biomarker biobanking

ESRD: End-stage renal disease; RRT: Renal replacement therapy; GFR: Glomerular filtration rate.

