2.9. Glucose-lowering effect will be measured by HbA1c and fasting blood glucose

# 3. Outcomes for the exploratory objectives:

- 3.1. Plasma volume will be estimated [ePV] by Strauss estimation:
  - a.  $([{Hb_{baseline}/Hb_{end}} \times {(100-Ht_{end})/(100-Ht_{baseline})}]-1) \times 100$
- 3.2. Relationship between proximal renal tubular natriuretic effects and volume reduction: proximal renal tubular natriuretic effects will be evaluated by lithium clearance FE(Li+); volume change will be measured using the following outcome:
  - a. Estimated plasma volume (ePV)
    - *i.* Estimated percent change by Strauss estimation
  - $([{Hb_{baseline}/Hb_{end}} \times {(100 Ht_{end})/(100 Ht_{baseline})}] 1) \times 100$
- 3.3. Relationship between proximal renal tubular natriuretic effects and kidney function: proximal renal tubular natriuretic effects will be evaluated by lithium clearance FE(Li+); Kidney function will be measured using measured GFR.
- 3.4. Relationship between volume and SNS activation: Volume will be measured by ePV. Hormones will be measured by:
  - a. Neurohormones: Plasma aldosterone and renin
  - b. SNS markers: norepinephrine, epinephrine, dopamine, heart rate, heart rate variability (SDNN and RMSSD)
- 3.5. Relationship between neurohormones and volume markers with kidney function. Hormones will be measured by serum aldosterone and renin. Volume will be measured by ePV. Absolute measure of renal function outcomes is measured by measured GFR.
- 3.6. Relationship between arterial stiffness and neuro-hemodynamic & volume markers. Arterial stiffness outcomes will be measured by radial, aortic and carotid AIx, carotid-radial PWV and carotid-femoral PWV. Neuro-hemodynamic and volume markers will be measured by:
  - a. Seated: SBP, DBP, and MAP
  - b. NICOM: SBP, DBP, and MAP (chronic change only)
  - c. SNS: epinephrine, norepinephrine, dopamine, heart rate, heart rate variability (SDNN and RMSSD)
  - d. Neurohormones: Plasma aldosterone and renin
  - e. Volume will be measured by ePV
- 3.7. Relationship between neurohormones & volume markers and blood pressure. Hormones will be measured by plasma aldosterone and renin. Volume will be measured by ePV. Seated and NICOM (chronic change only) measures of SBP, DBP, and MAP will be the blood pressure outcomes.
- 3.8. The blood and urine biomarkers are:
  - a. Plasma chemistry:
    - *i.* Sodium, potassium, urea, phosphate, chloride, calcium
    - ii. AST, ALT, ALP, amylase

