# 2. Analysis for secondary objective:

- 2.1. The numbers of hypoglycemic episodes, acute rejection episodes, volume depletion, UTI or genital infection, acute kidney injury, ketoacidosis and serious adverse events will be reported for both the placebo group and dapagliflozin group. No statistical comparisons will be performed.
- 2.2. 2.10. The same models described in the analysis of primary objective 1.1 will be completed for each of the different outcomes.

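### Read literally, the recording rule keeps non-serious hyperkalaemia that does not stop treatment out of the adverse events, and neither document plans a count of it by arm

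*Protocol*

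**What the plan says.** Three parts of the protocol treat hyperkalaemia as something to be collected.

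- Section 9.1.2, safety outcomes: "Adverse events include AKI, volume depletion, hyperkalemia, urinary and mycotic infections, ketoacidosis, amputations and allergic reactions".
- Table 3, adverse-events column: "volume depletion, Hyper-kalemia, acute kidney injury, urinary infections, mycotic infections, amputation, allergic reaction, hypo-glycaemia, ketoacidosis".
- Section 9.1.2, on where events go: "All adverse events will be recorded on case report forms".

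Section 10.3 then sets a filter for laboratory findings. It says that deterioration in "protocol-mandated laboratory values, or vital signs should therefore only be reported as AEs if they fulfil any of the SAE criteria". The sentence goes on to two further routes: the change is why study treatment was stopped, or it meets the criteria for an AE of special interest. Where there are symptoms, the symptom is the reported event and the laboratory value is supporting information. The sentence before the filter says that mandated laboratory results will be summarised in the study report.

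Section 10.2.3 lists urinary and genital infections, ketoacidosis, volume depletion, fractures, major hypoglycaemia, acute kidney injury and amputation. Hyperkalaemia is not there, and no potassium limit appears anywhere in the documents.

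SAP 2.1 plans these safety counts: "The numbers of hypoglycemic episodes, acute rejection episodes, volume depletion, UTI or genital infection, acute kidney injury, ketoacidosis and serious adverse events will be reported". Potassium appears in the SAP as an exploratory plasma chemistry outcome (3.8: "Sodium, potassium, urea, phosphate, chloride, calcium"), analysed with the same mixed model as blood pressure. Protocol section 11 tabulates adverse-event frequency without comparison.

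**The concern.** The protocol promises hyperkalaemia as a safety outcome and then applies a rule that screens out the kind of case a scheduled blood test would usually find: a raised potassium with no symptoms, no serious outcome and no change to treatment. Acute kidney injury, also a laboratory event, passes the same filter because 10.2.3 lists it with a creatinine criterion. Nothing suggests that the different handling of potassium was intended.

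The population makes the omission matter. Section 2.4 states that capturing safety signals is an important aim and describes electrolyte disturbances with calcineurin inhibitors. Section 6.2 allows ACE inhibitors and ARBs throughout and relies on frequent monitoring to detect problems with the combination. A low hyperkalaemia count could be read as reassurance when it partly reflects the recording rule.

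**Working it through.** The plan gives no figure on this point, so the check traces each type of case through the documents. Two readings are assumed: potassium is a protocol-mandated test, and the special-interest events in 10.3 are the list in 10.2.3.

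| Type of case | Recorded as an AE under 10.3? | Where it would be reported |
|---|---|---|
| Serious | Yes | Inside the SAP 2.1 serious-event total and the section 11 tabulation; no hyperkalaemia line in SAP 2.1 |
| Not serious, but the reason for stopping treatment | Yes | Section 11 tabulation; no line in SAP 2.1 |
| Not serious, symptomatic, treatment continued | The symptom is; potassium is supporting information | Under the symptom |
| Not serious, no symptoms, treatment continued | No | Only in the laboratory summary (form unstated) and the SAP 3.8 mean-change model |

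The last row conflicts with 9.1.2 and Table 3.

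**Possible size of the under-count.** The documents give no hyperkalaemia rate, so the rates below are assumptions. Let n = 52 (protocol 5.3), p = the proportion of participants with hyperkalaemia, and s = the share of cases that are serious or stop treatment. Then expected cases = n × p, expected recorded = n × p × s, and the chance that none is recorded = (1 − p × s)^52.

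| p | Expected cases | Expected recorded, s = 0 to 20% | Chance none recorded, s = 0 to 20% |
|---|---|---|---|
| 5% | 52 × 0.05 = 2.6 | 0 to 0.52 | 100% to 59% |
| 10% | 52 × 0.10 = 5.2 | 0 to 1.04 | 100% to 35% |
| 20% | 52 × 0.20 = 10.4 | 0 to 2.08 | 100% to 12% |

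For example, at p = 10% and s = 20%: 5.2 × 0.20 = 1.04, and (1 − 0.02)^52 = 0.35.

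**Whether the mean model would show it.** Suppose 3 of 26 participants in one arm rise by 1.0 mmol/L and the rest do not change. That arm's mean moves by 3/26 × 1.0 = 0.115 mmol/L. With 24 per arm (protocol 5.3) and an assumed SD of change of 0.3 to 0.5 mmol/L, the approximate 95% half-width for the difference in means is t(0.975, 46) × SD × √(2/24):

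- SD 0.3: 2.013 × 0.3 × 0.289 = 0.17 mmol/L
- SD 0.5: 2.013 × 0.5 × 0.289 = 0.29 mmol/L

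A shift of 0.115 lies inside both, so three marked rises in one arm could pass unnoticed in a comparison of means. The SAP 3.8 models also use only Visits 3, 4 and 9. Any potassium measured at another visit would not enter them.

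**The case against.** The best reply is that several routes stay open. Serious and treatment-stopping cases are recorded, SAP 2.1 counts serious events, section 11 tabulates whatever is recorded, and 10.3 promises a laboratory summary, which is its stated reason for keeping laboratory changes out of the AE list. All of that is correct. A reader might infer that the trial would report no hyperkalaemia however many cases occurred, or that SAP 3.8 is the only place it could appear. The documents do not support either inference. What remains is that none of these routes is a planned count of hyperkalaemia by arm, and section 11 can tabulate only what has passed the 10.3 filter.

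A site might also follow 9.1.2 and Table 3 rather than 10.3, or, since 10.3 elsewhere prefers a diagnosis to a list of symptoms, enter a symptomatic case as hyperkalaemia. That is possible, so under-recording is not certain. But sites choosing differently between conflicting instructions would make the counts inconsistent.

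The point depends on potassium being protocol-mandated. The laboratory columns of Table 3 are broken in the available text, so this is inferred from SAP 3.8. For a non-mandated test, 10.3 asks for clinically relevant deterioration to be reported even without symptoms, and the point would weaken.

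Three extensions are tempting but go too far:

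- Section 7.6.1 says of phosphate: "Higher proportions of patients with marked laboratory abnormalities of hyperphosphatemia were reported in dapagliflozin vs placebo". This is background risk. Hyperphosphataemia is not a safety outcome in 9.1.2, so no promised outcome is lost.
- Table 2 schedules blood samples at weeks 6 and 13 but names no analytes by visit, and the SAP notes that urea was not collected at Visit 4. Potassium at weeks 6 and 13 cannot be assumed.
- Other events that SAP 2.1 does not name are mostly covered elsewhere: deaths are serious events, and recorded AEs fall under section 11.

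**Conclusion.** The point holds as an inconsistency that would under-count a named safety outcome. Under 10.3 as written, non-serious hyperkalaemia that does not stop treatment is not recorded as an AE, and neither document plans a count by arm or defines the event. This rests on a literal reading of 10.3, on equating its special-interest events with the 10.2.3 list, and on potassium being a mandated test.

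The size cannot be fixed from the documents. Under the assumed rates, at least four in five cases would go unrecorded as hyperkalaemia (s no higher than 20%), yet the chance of recording none falls as low as 12%. The defect is therefore under-counting rather than certain silence. It affects a descriptive safety item and leaves the primary blood pressure analysis untouched. It should be corrected, because safety is the first secondary objective and the correction is cheap.

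**What to change.** In the protocol, reconcile 10.3 and 10.2.3 with 9.1.2 and Table 3 by adding hyperkalaemia to the 10.2.3 list, with a definition that the trial team sets before unblinding.

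In the SAP, add to 2.1 a descriptive count by arm of participants with any post-baseline potassium above that limit, using every visit at which potassium was measured and stating which visits those are. In keeping with the rest of SAP 2.1, no test is needed.

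The cost is one list entry, slightly more AE recording at the site and one extra table. If the protocol change comes too late to affect recording, the SAP table alone would still recover the count from the potassium results held, provided the limit is fixed before unblinding.

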10.5 Suspected unexpected serious adverse reactions (SUSARs)

Adverse reactions are all untoward and unintended responses to an investigational product related to any dose administered. Unexpected adverse reactions are SUSARs if the following three conditions are met:

- 1. the event must be serious;
- 2. there must be a certain degree of probability that the event is a harmful and an undesirable reaction to the medicinal product under investigation, regardless of the administered dose;
- 3. the adverse reaction must be unexpected, that is to say, the nature and severity of the adverse reaction are not in agreement with the product information as recorded in:
 - Summary of Product Characteristics (SPC) for an authorised medicinal product;
 - Investigator's Brochure for an unauthorised medicinal product.

Health Authority and METC Reporting

SUSARs will be reported to the accredited ethics committee and recorded in an overview list. When needed, they will be also reported expedited to the appropriate health authority (Health Canada).

In an emergency, unblinding can be performed to identify the treatment given to that subject. Unblinding is not to be performed for any reason, other than an emergency where unblinding is required. When the Investigator unblinds the subject he/she must note the date, time and reason for removing it and record this information in the Comments section of the CRF and in the source data. He/she must also immediately inform the project leader/principal investigator about the unblinding of the subject treatment. Even though the subject has been unblinded, any blood samples for safety or pharmacodynamic assessments will continue to be drawn, for at least 24hr following the last dose as long as doing so will not compromise subject welfare. It is the responsibility of the Principal Investigator to ensure the investigator site staff are appropriately

trained on the unblinding procedure in case of emergency. Study drug must be discontinued after unblinding but the subject will be followed until resolution of the adverse event. It is the intent that subjects who discontinue treatment with the study drug will continue in the study according to the visit schedule. At the conclusion of the study, the occurrence of any unblinding can be reported.

